8.4 Overdose

For this study, any dose of benralizumab greater than 200 mg will be considered an overdose.

There is no specific treatment for an overdose with benralizumab. If overdose occurs, the participant should be treated supportively with appropriate monitoring as necessary.

- An overdose with associated AEs is recorded as the AE diagnoses/symptoms on the relevant AE modules in the CRF and on the Overdose eCRF module.
- An overdose without associated symptoms is only reported on the Overdose eCRF module

If an overdose on an investigational product or AstraZeneca non-investigational product occurs in the course of the study, the Investigator or other site personnel inform appropriate AstraZeneca representatives immediately, but **no later than 24 hours** of when he or she becomes aware of it.

The designated AstraZeneca representative works with the investigator to ensure that all relevant information is provided to the AstraZeneca Patient Safety data entry site within one or 5 calendar days for overdoses associated with an SAE (see section 8.3.8) and within 30 days for all other overdoses.

8.5 Human Biological Samples

Note: following the approval of Amendment 4 (CSP version 5), no further human biological samples as described in this section will be collected.

Instructions for the collection and handling of biological samples will be provided in the study specific laboratory manual. Samples should be stored in a secure storage space with adequate measures to protect confidentiality. For further details on Handling of Human Biological Samples see Appendix C.

Samples will be stored for a maximum of 15 years from the date of the issue of the Clinical Study Report in line with consent and local requirements, after which they will be destroyed/repatriated.

- Pharmacokinetic samples will be disposed of after the Bioanalytical Report finalization or 6 months after issuance of the draft Bioanalytical Report (whichever is earlier), unless consented for future analyses.
- Pharmacokinetic samples may be disposed of or anonymized by pooling. Additional analyses may be conducted on the anonymized, pooled pharmacokinetic samples to further evaluate and validate the analytical method. Any results from such analyses may be reported separately from the Clinical Study Report.

• Remaining anti-drug antibody sample aliquots will be retained at AstraZeneca or its designee for a maximum of 5 years following issue of the Clinical Study Report. Additional use includes but is not limited to further characterization of any anti-drug antibodies, confirmation and/or requalification of the assay as well as additional assay development work. The results from future analysis will not be reported in the Clinical Study Report.

8.5.1 Pharmacokinetics

- Serum samples will be collected for measurement of serum concentrations of benralizumab as specified in Table 1. It is important that the date, time, and location of each SC injection is recorded for each participant.
- Pharmacokinetic samples will be collected before administration of investigational product, if applicable.
- Samples may be collected at additional time points during the study if warranted and agreed upon between the investigator and the sponsor, eg, for safety reasons. The timing of sampling may be altered during the course of the study based on newly available data (eg, to obtain data closer to the time of peak or trough matrix concentrations) to ensure appropriate monitoring.
- Any changes in the timing or addition of time points for any planned study assessments must be documented and approved by the relevant study team member and then archived in the AstraZeneca and site study files, but will not constitute a protocol amendment
- Samples collected for analyses of benralizumab concentration may also be used to evaluate safety or efficacy aspects related to concerns arising during or after the study.
- Samples will be collected, processed, labelled, stored, and shipped as detailed in the Laboratory Manual.
- The IRB/IEC will be informed of any safety issues that require alteration of the safety monitoring scheme or amendment of the ICF.

8.5.1.1 Determination of Drug Concentration

Samples for determination of drug concentration in serum of patients that received benralizumab will be assayed by bioanalytical test sites operated by or on behalf of AstraZeneca, using an appropriately validated bioanalytical method. Full details of the analytical method used will be described in a separate bioanalytical report.

The bioanalytical laboratory will have access to the randomization list. Drug concentration information that may unblind the study will not be reported to investigative sites or blinded personnel until the study has been unblinded.

Incurred sample reproducibility analysis, if any, will be performed alongside the bioanalysis of the test samples. The results from the evaluation, if performed, will be reported in a

separate Bioanalytical Report.

8.5.2 Immunogenicity Assessments

Blood samples for determination of anti-drug antibodies in serum will be collected pre-investigational product administration as detailed in Table 1 and assayed by bioanalytical test sites operated by or on behalf of AstraZeneca, using an appropriately validated bioanalytical method. Full details of the methods used will be described in a separate report.

Anti-drug antibodies samples may also be further tested for characterization of the anti-drug antibody response.

Samples will be collected, labelled, stored, and shipped as detailed in the Laboratory Manual.

8.5.3 Pharmacodynamics

Blood and urine samples will be collected for pharmacodynamic measurements at timepoints specified in Table 1.

For information on storage, re-use, and destruction of pharmacodynamic samples see Section 8.5 and Appendix C.

8.6 Human Biological Sample Biomarkers

8.6.1 Collection of mandatory samples for biomarker analysis

Note: following the approval of Amendment 4 (CSP version 5), no further human biological samples as described in this section will be collected.

Mandatory collection of samples for exploratory biomarker research is a part of this study. Samples for exploratory biomarker research are required and will be collected from all participants in this study as specified in Table 1. Blood (whole blood, serum, and plasma) as well as stomach and/or intestinal tissue will be collected. Samples will be tested in order to evaluate the effect of benralizumab on gene expression (RNA transcript analysis), inflammation, and immunological mechanisms related to the pathogenesis of EG/EGE.

Instructions for sample collection, processing, storage, and shipment are provided in the Laboratory Manual. Results from the exploratory biomarker analyses, if performed, will be reported separately from the CSR. (Investigators will not receive the results.)

8.6.1.1 Serum

Serum samples will be collected as specified in Table 1 to evaluate the pharmacology of benralizumab as well as biomarkers of eosinophil recruitment, activation, and survival (eg, absolute eosinophil count, CCI). Additional markers of cellular inflammation and/or activation may be assessed including, but not limited to, those associated with humoral

autoimmunity (total serum IgE), T cell subsets (eg, CCI), eosinophil granule proteins (eg, CCI), epithelial cell damage (eg, CCI), or activation of inflammatory cells including CCI.

The results from such studies will not be reported in the CSR but in separate reports or publications as appropriate.

Serum samples will be collected according to the schedules presented in Table 1 for analysis of serum tryptase levels. The analysis will be performed at the central laboratory.

Instructions for sample collection, processing, storage, and shipment will be found in the Laboratory Manual.

8.6.1.2 Tissue Histology and Immunostaining

Biopsies will be collected at screening, Week 24, and Week 52. Biopsies will be taken from sites within the stomach and/or small intestine identified during endoscopy by site physicians. At the time of each EGD, pts will also have biopsies taken of the esophagus, 2 each proximal and distal, for monitoring of esophageal eosinophilia during the trial.

Biopsies will be collected and processed locally at the clinical sites as described in detail in the Laboratory Manual.

Staining of the biopsies will be conducted at an appropriate contract lab and/or at AstraZeneca. The gastrointestinal biopsies will be stained for chemical markers for the detection and enumeration of inflammatory cell types such as eosinophils, mast cells, and basophils. Other molecules that may be directly or indirectly involved in the mechanism of action of benralizumab (including, but not limited to, or indirectly involved in the mechanism of and/or the pathophysiology of EG/EGE may be investigated.

8.6.1.3 RNA Transcriptome Research

Transcriptome studies (blood and biopsy) will be conducted. Transcriptomic studies of serum and/or biopsies collected from gastrointestinal mucosal tissue will be conducted using microarray, RNA-sequencing, and/or alternative equivalent technologies, which facilitate the simultaneous measurement of the relative abundances of as many as thousands of RNA species, resulting in a transcriptome profile for each tissue sample. This will enable the evaluation of transcriptome profiles that will provide molecular insight into mechanisms underlying tissue pathology, identification of features associated with pathology conserved across subjects or across areas of the GI tract within a given subject, as well as the mechanism of action of benralizumab and how its clinical efficacy correlates with changes in gastrointestinal tissue transcriptome.

Details on biopsy acquisition and processing for transcriptomics will be included in the lab manual.

8.7 Optional Genomics Initiative Sample

Collection of optional samples for Genomics Initiative research is also part of this study and is subject to a separate consent in the ICF addendum, and local regulations.

A blood sample for DNA isolation will be collected from adult participants who have consented to participate in the genetic analysis component of the study at Visit 2 (Table 1). Adolescents are not included in this option. Participation is optional; participants who do not wish to participate in the genetic research may still participate in the study. Samples can be collected at any time after the ICF has been signed.

Details on processes for collection, shipment, storage and destruction of these samples are provided in Appendix D and in the Laboratory Manual.

8.8 Healthcare Resource Utilization

EG/EGE-related and other GI-disease complications-related healthcare resource utilization data will be collected in the eCRF by the Investigator and study-site personnel for all participants throughout the study. Protocol-mandated visits, procedures, tests, and encounters are excluded.

At visits when healthcare use is being collected, as specified in Table 1 through Table 3, the Investigators retrospectively collect any EG/EGE-related and other GI disease complications-related healthcare resource utilization information. At baseline, healthcare resource utilization will be collected with a 6-month recall period. At all subsequent visits, any EG/EGE-related and other GI disease complications-related healthcare resource utilization information will be collected with a recall period of 'since last HRU assessment during the scheduled visit'.

The data collected may be used to conduct exploratory economic analyses and will include:

- Number and duration of medical care encounters, including surgeries, and other selected procedures (inpatient and outpatient)
- Duration of hospitalization (total days or length of stay, including duration by wards [eg, intensive care unit])
- Outpatient medical encounters and interventions (including specialist visits, General Practitioner visits, home health care visits, and emergency room visits, etc.)
- Number and type of diagnostic and therapeutic tests and procedures

9 STATISTICAL CONSIDERATIONS

The analysis of the study will be performed when all patients have completed their last visit in the study. Data from this analysis will be summarized in a synoptic CSR.

9.1 Statistical Hypotheses

No hypothesis testing will be performed given the decision to terminate recruitment to the study, resulting in the intended sample sizes required not being recruited.

9.2 Sample Size Determination

The original sample size calculations for the study were based on the change from baseline in SAGED score at Week 24 dual primary endpoint. Changes in the other dual primary histological response rate endpoint required smaller sample sizes as larger relative differences are assumed (10% placebo response versus 80% benralizumab response).

Part A intended to enroll approximately 50 patients with EG (with or without duodenal involvement). Eligible patients with duodenal only disease were also to be included whilst enrolling the required 50 EG patients, with no minimum requirement on the number of duodenal only patients. A minimum of 60 and a maximum of 80 patients in the overall population in Part A were targeted. Thirty patients per arm in the overall population, and 25 patients per arm with gastric disease would provide >85% and >80% power for statistical significance at the 10% 2-sided level for each population respectively, if the true treatment effect for the change from baseline in SAGED score is a standardized effect size (difference in means/ standard deviation) of 0.75. A standardized effect size is used as the variability of the SAGED score is not known yet. An effect size of 0.75 is a similar relative effect size as that observed in the antolimab Phase 2 trial (Dellon et al 2020). Approximately 20 adolescent patients (12 to 17 years of age) with either EG or duodenal only disease were targeted for inclusion in Part A.

The final sample size for the study is limited to 12 patients due to closure of recruitment to the study.

9.3 Populations for Analyses

The following populations are defined:

Table 10 Populations for Analysis

Population/Analysis set	Description
Enrolled	All participants who sign the ICF
All patients analysis set	All patients screened for the study, to be used for reporting of disposition and screening failures
Safety analysis set	The safety analysis set consists of all patients who have received at least one dose of investigational product.
	Erroneously treated patients (eg, those randomized to one treatment but actually given the other treatment) are accounted for in the treatment group of the treatment they actually received. A patient who has on one or several occasions received active

Population/Analysis set	Description
	investigational product is classified as active. Safety summaries will be based on this analysis set and for whom any post-dose data are available.
Open-label benralizumab analysis set	All patients who receive at least 1 dose of benralizumab after the end of the double-blind treatment period

9.4 Statistical Analyses

Analyses will be performed by AstraZeneca or its representatives. Any deviations from the analyses outlined here will be reported in the CSR.

9.4.1 General Considerations

As recruitment to the study has been terminated and the final sample size is too low to perform originally planned analysis, analyses will consist of descriptive summaries and figures of safety data for the double-blind placebo-controlled period (Part A) and the openlabel periods (Parts C and D) as well as select patient listings of demographic and baseline characteristics, safety and key efficacy data. No statistical analyses or hypothesis testing will be performed.

All available data will be included in data presentations, regardless of use of rescue therapy, restricted medications for EG/EGE or treatment discontinuation.

9.4.2 Efficacy

All available (from Part A and Part C) peak eosinophil count (eos/hpf) data will be listed by patient including whether patients achieved a histological response at available visits, defined as ≤ 6 eosinophils/hpf in the stomach and/or, ≤ 15 eosinophils/hpf in the duodenum, as applicable based on disease area involvement at enrollment.

All available (from Parts A and C) SAGED score data will be listed by patient including individual abdominal pain, nausea, bloating, early satiety and loss of appetite severity item scores and the bi-weekly SAGED score calculated as the 14-day mean of the daily sum of the item scores.

Listings of other efficacy endpoints may be produced as required including all available data from Parts A, C, and D. Individual patient data may be presented graphically as appropriate.

Available efficacy data collected in relation to EG-REFs, EoD-REFs, PGI-S/C, CGI-S/C will be listed by patient (from the point of protocol amendment onwards only PGI-C data is collected during Part D but data already collected from patients in Part C will be included as available).

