^c For patients who are self-administering IP, these visits can optionally be conducted remotely by telephone contact.

d In adult participants at select sites.

To be completed at the discretion of the Sponsor and in accordance with guidance in Section 7.2.

											CSP Section
Visit (V)	V20	V21a	V22ª	V23	V24ª	V25ª	V26 EOT	Unscheduled	IP discontinuation (Section 7)	Follow-up ^b	
Week	R+4	R+8	R+12	R+16	R+20	R+24	R+28	-	4 weeks post-dose	8 weeks post-dose	
Visit Window (Days)	± 3	± 3	± 3	± 3	± 3	± 3	± 3		± 3	± 7	
General procedures											
Informed consent/assent	X	-	-	-	-	-	-	-	-	-	Appendix A 3
Return PRO device	X	-	-	-	-	-	-	-	-	-	8.2.1
Efficacy assessments						•	•				
Clinical Global Impression of Severity	X	X	X	X	X	X	X	-	X	-	8.1.5
Diet questionnaire	X	-	-	-	-	-	X	X	X	-	8.1.6
Healthcare resource utilization	X	-	-	-	-	-	X	-	X	-	8.8
Safety assessments						•					
Adverse events	X	X	X	X	X	X	X	X	X	X	8.3
Concomitant medication	X	X	X	X	X	X	X	X	X	X	6.5
Complete (brief) physical exam	-	-	-	-	-	-	X	(X)	X	-	8.2.1
Vital signs	-	-	-	-	-	-	X	X	X	-	8.2.2
Laboratory assessments					•						
Hematology/clinical chemistry	-	-	-	-	-	-	X	-	X	X	8.2.4
Urine pregnancy test ^c	-	-	-	-	-	-	X	-	X	X	8.2.5
Investigational product admini	stration				·	ı	ı	,			•
Administration	X	X d	X d	X	X d	X d	-	_	-	-	6.1.3

EOT: end of treatment; IP: investigational product. R: reference visit number of weeks (ie, number of weeks for the visit prior to approval of Amendment 4).

^a For patients who are self-administering IP, these visits can be conducted remotely by telephone contact.

Can be conducted remotely by telephone contact

^c Patients should be strongly encouraged to monitor for pregnancy during the study and report a pregnancy to the site as soon as possible.

d Optional at-home or remote location self-administration (Section 6.1.3.5).

Table 4 presents the schedule of activities for patient-reported outcomes prior to approval of Amendment 4. There will be no further collection of patient-reported outcome data following Visit 20 of Part D.

	During s	chedule	d clinic	visits		At home		CSP Section
	Run-in	Trea	tment p	eriod	Run-in, do	uble-blinded and	open-label	
Visit (V) (if applicable)	V1	V2	V8	V15				
Week ^a /Frequency	-8 to -4	0	24	52	Every evening from V1 until V20 ^b	Every 2 weeks from V1 until V20c	Every 4 weeks after V2 until V20c	
Symptom Assessment for Gastrointestinal Eosinophilic Diseases (SAGED)	-	-	-	-	X	-	-	8.1.3.1
Bristol Stool Form Scale	-	-	-	-	X	-	-	8.1.3.2

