		•	Change from baseline in proportion of vomiting- free days, and change from baseline in frequency of vomiting episodes at Week 24
		•	Change from baseline in proportion of diarrhea- free days, and change from baseline in frequency of diarrhea episodes at Week 24
		•	Change from baseline in proportion of days both diarrhea and constipation free at Week 24
		•	Time to clinically meaningful improvement in SAGED score
		•	Change from baseline in PROMIS Fatigue 7a score and PAGI-SYM score at Week 24
•	Part A: To compare the effect of benralizumab 30mg Q4W with placebo on rescue corticosteroid use	•	Key ^b : Proportion of patients with no rescue corticosteroid use up to Week 24
•	Part A: To compare the effect of benralizumab 30 mg Q4W with placebo on health-related	•	Change from baseline in SF-36v2 PCS and MCS at Week 24
	quality of life in patients with EG/EGE	•	Change from baseline in PAGI-QoL at Week 24
•	To assess the pharmacokinetics and immunogenicity of benralizumab in patients with EG/EGE	•	Serum benralizumab concentration over time Anti-drug antibodies over time
Saf	ety	 	
•	To assess the safety of benralizumab in patients with eosinophilic gastritis and/or gastroenteritis	•	Adverse Events, vital signs, physical exam, and laboratory parameters

Table 6 Objectives and Endpoints

Objectives	Estimand description/Endpoint
Exploratory	
Part A: To describe the effect of benralizumab on clinical features of EG/EGE and disease activity	Change from baseline in vomiting severity at Week 24
	Change from baseline in diarrhea severity at Week 24
	Change from baseline in endoscopic measures of inflammation and remodeling, EG-REFS, by central reader at Week 24
	Change from baseline in PAGI-SYM, DSQ, PGIS, PGI-C, CGI-S, and CGI-C
Part D: To collect more information on the safety and clinical response of benralizumab in EG/EGE.	Adverse Events, vital signs, physical exam, and laboratory parameters
	Change from baseline in CGI-S

Only restricted medications given that are considered to have a potentially meaningful impact on EG/EGE outcomes will be considered intercurrent events.

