8.1.2 Endoscopic Reference System Scores

Note: following the approval of Amendment 4 (CSP version 5), there are no study-mandated endoscopy procedures. The text below concern assessments prior to implementation of Amendment 4.

During study-mandated endoscopy procedures, the endoscopic manifestations of EG/EGE, including erosions/ulcerations, granularity, raised lesions, erythema, friability, fold thickness and pyloric stenosis, will be scored by the endoscopist using the Eosinophilic Gastritis Endoscopic Reference System (EG-REFS) from three areas of the stomach (antrum, body, and fundus). Endoscopic appearance of the duodenum will also be characterized.

The Eosinophilic Esophagitis Endoscopic Reference System (EREFS) is a scoring system for assessing the presence and severity of major endoscopic findings in the esophagus, including

esophageal edema, rings, exudates, furrows, and stricture. A global (EREFS) should be obtained that scores the most severe esophageal abnormality in the criteria scoring system.

Each of these GI scoring tools will have an additional separate overall global disease activity scoring assessment (0 normal –10 extremely diseased).

The EGREFS including duodenal findings and EREFS will be centrally-read from video recordings and Investigator-read during the upper endoscopies. Centralized imaging data assessments and scoring from expert physician review will be performed for all endoscopies. Standardized methods for training Investigators on the application of these scoring systems to ensure the collection of quality data using this measure will be implemented. Details on the scoring will be provided to Investigators in a separate manual.

The sites will remove patient-identifying information from the imaging data header prior to sending the imaging data to the central reader.

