8.1.3 Patient Reported Outcomes

Note: following the approval of Amendment 4 (CSP version 5), participants will cease performing PRO assessment at their next clinic visit (ie, Part D Visit 20) and return their handheld PRO devices. The text below concern PRO assessments prior to implementation of Amendment 4.

Participants will complete all PRO assessments using a handheld device. The handheld device (or the web-based backup, in case of device failure) will be the only accepted source of PRO data. Participants will be required to complete a training module before taking the device home. The Investigator will ensure that participants are properly trained on the use of this device and the importance of completing assessments as scheduled. The handheld device will be programmed at Visit 1 with reminder alarms for the daily PROs. Study site staff will be able to adjust alarms for specific participant needs as required.

The Investigator or designee will be responsible for monitoring participant adherence with the daily PROs and follow-up as necessary to minimize missing data. Participant compliance should be checked weekly (at a minimum) to ensure that the participant is completing the assessments as scheduled. Monitoring of participant adherence to the daily PROs is especially critical between Visit 1 and Visit 2 to ensure that the participant meets applicable criteria for randomization. If the participant does not meet the randomization requirements, the device will be deactivated and retained at the site for future use.

Participants are expected to bring the device to every Part A site visit. To reduce bias, review of compliance with the assessments, completion of any available assessments, and logging of the visit on the handheld device should be completed prior to any other study procedures. Compliance with the assessment schedule should be reviewed weekly throughout the study.

Participants with low compliance should be reminded to complete their assessments through follow-up phone calls and during site visits. Correcting poor compliance is required to ensure sufficient data are available for supporting the dual-primary endpoint of this study.

The timing and frequency for each PRO is presented Table 4. PRO assessments end at Visit 21 when the handheld device will be returned to the study site.

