8.1.4 Clinical Global Impression of Severity

Clinical Global Impression of Severity (CGI-S) is a single item designed to capture the clinician's perception of the participant's overall disease severity at the time of the visit using a 6-point categorical response scale (no signs and/or symptoms to very severe signs and/or symptoms).

The answer will be entered in the eCRF at Week 0 and Week 24 of Part A (Table 1) and all visits in Part D (Table 3).

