8.1.5 Clinical Global Impression of Change

Note: following the approval of Amendment 4 (CSP version 5), investigators will cease assessing the Clinical Global Impression of Change.

Clinical Global Impression of Change (CGI-C) is a single item assessment to capture the clinician's perception of change in the participant's health status. The clinician is asked to report the degree to which the participant has changed since entering the treatment period during the randomization study period using a 7-point scale (very much improved, much improved, minimally improved, no change, minimally worse, much worse, very much worse). For the open label extension period, the clinician will report the degree to which the participant has changed since entering the open label extension period.

The answer will be entered in the eCRF at Part A and Part C visits as described in Table 1 and Table 2.

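### Does naming PGI-C instead of CGI-S as the Part D rating, together with out-of-date SAP response lists, call for a change to the plan?

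*Protocol*

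**What the plan says.** **Part D rating.** Protocol 9.4.2 says that available EG-REFS, EoD-REFS, PGI-S, PGI-C, CGI-S and CGI-C data will be listed by patient. It then adds in parentheses that "from the point of protocol amendment onwards only PGI-C data is collected during Part D".

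Other current protocol text says something different:

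- Section 8.1.4 has CGI-S recorded at Week 0, then "Week 24 of Part A (Table 1) and all visits in Part D (Table 3".
- Table 3 has a CGI-S row marked at V20 to V26 and at the IP discontinuation visit. It has no row for PGI-S, PGI-C or CGI-C. The CGI-S row cites Section 8.1.5, which is CGI-C, instead of 8.1.4.
- Table 6 gives "Change from baseline in CGI-S" as the clinical-response endpoint for Part D.
- The lead-in to Table 4 states: "There will be no further collection of patient-reported outcome data following Visit 20 of Part D". The note at the head of 8.1.3 agrees: "participants will cease performing PRO assessment at their next clinic visit (ie, Part D Visit 20". Lower down, 8.1.3 also says "PRO assessments end at Visit 21 when the handheld device will be returned to the study site".
- Section 8.1.5 says "investigators will cease assessing the Clinical Global Impression of Change", and 8.1.2 says "there are no study-mandated endoscopy procedures" after Amendment 4.

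**Response lists.** Protocol 8.1.3.9 gives PGI-S four options. SAP 4.2.18.1 gives it six, scored 1 to 6. SAP 4.2.20.1 defines the CGI-S scale by reference to that PGI-S list. SAP 4.2.21.1 defines CGI-C by reference to the PGI-C list, whose wording differs from Protocol 8.1.5. SAP Table 11 keeps listings of all four ratings over the double-blind and open-label periods.

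**The concern.** The sentence sits in the analysis section of the current protocol, so the amendment log does not explain it away. Read literally, it says that Part D yields a patient rating that is no longer collected, and it passes over the one clinical-response rating that is. A programmer working only from 9.4.2 might look for PGI-C after Visit 20 and find none, or might leave the Part D CGI-S values out of the listing. The wrong cross-reference in Table 3 points the same way.

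The SAP lists raise a separate worry. If stored codes were turned into labels through SAP 4.2.18.1 or 4.2.21.1, a listing could show options that the patient or clinician was never offered. With hypothesis testing dropped, the listings are the efficacy record for these ratings, so correct labels matter.

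**Working it through.** There is no planned figure to reproduce. The check compares the passages and counts.

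**1. Which of the six measures in 9.4.2 continue in Part D?**

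| Measure | After Amendment 4 | Source |
|---|---|---|
| EG-REFS, EoD-REFS | no mandated endoscopy | Protocol 8.1.2 |
| PGI-S, PGI-C | stop at V20 | Protocol 8.1.3, Table 4 lead-in |
| CGI-C | stopped | Protocol 8.1.5 |
| CGI-S | V20 to V26 and IP discontinuation | Protocol 8.1.4, Table 3 |

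6 − 2 − 2 − 1 = 1 continues: CGI-S. The instrument named in 9.4.2 is therefore wrong.

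**2. Does the slip lose any CGI-S value?** Sites collect according to Table 3, which is unambiguous on this point. Four places bear on the listing:

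- the main clause of the same sentence in 9.4.2 includes CGI-S;
- Protocol 9.4.1 presents all available data;
- SAP 3.3.3 lists all collected data, unscheduled visits included;
- SAP Table 11 lists CGI-S over DB + OLE.

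If all 12 randomized patients entered Part D (an upper bound; the number is not stated), there would be 12 × 7 = 84 scheduled CGI-S ratings at V20 to V26. All fall under these rules, so the number shown to be missing from a planned output is 0.

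**3. Visit 21.** The sentence in 8.1.3 stands below a note saying that the text which follows describes practice before Amendment 4. Under that schedule Visit 21 was Week 76 (SAP 4.2.2.1). The current rule, Visit 20, is in the note itself. There is nothing to reconcile.

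**4. PGI-S.** The SAP scores are 1 no symptoms, 2 very mild, 3 mild, 4 moderate, 5 severe, 6 very severe. The instrument has none, mild, moderate and severe. The result depends on how responses are stored, which the documents do not state:

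- Stored as text: 0 of 4 labels wrong. The SAP scores would be 1, 3, 4, 5, so none to severe spans 5 − 1 = 4 points, against 4 − 1 = 3 with consecutive codes. This matters only if scores are shown.
- Stored as 1 to 4 and decoded through the SAP list: codes 2, 3 and 4 become very mild, mild and moderate, so 3 of 4 are wrong.
- Stored as 0 to 3 and decoded that way: 3 wrong and 1 without a label.

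The score table served the Week 24 change from baseline in SAP 4.2.18. That summary is not in Table 11, and SAP Section 8 retires analyses outside that table. It carries over only principles relating to the retained outputs, with period definitions as its example. Nothing tells the programmer to recode a listing through 4.2.18.1.

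**5. CGI-C.** Both lists have seven ordered positions with no change at position 4, so codes 1 to 7 keep their rank and direction. The labels differ at the other 7 − 1 = 6 positions, mostly as near-synonyms. The clearest clash is much worse, which is sixth in Protocol 8.1.5 and seventh in the SAP list. It matters only if labels are reapplied from the SAP.

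**6. CGI-S.** Both documents give six points. The SAP's link to PGI-S would cause an error only if the PGI-S list were cut to four without separating CGI-S.

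**The case for a change.** The strongest case for acting is that every mismatch can be verified in current text, that the SAP addendum supplies no replacement response lists, and that correction is cheap: an instrument name, a cross-reference and the response lists, with no new data. It can also be said that the analysis section should not misstate the sole clinical-response measure of Part D, and that SAP 4.2.20.1, which still gives CGI-S at Weeks 0 and 24 only, does not repair it.

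The inconsistencies stand. Their consequence does not. The remark in 9.4.2 describes data collection in passing; it neither sets the schedule nor restricts the listing. SAP 4.2.20.1 describes the collection that fed the retired Week 24 change and does not limit what Table 11 lists. Spelling out the Part D visits for the CGI-S listing would repeat what SAP 3.3.3 and Table 11 already require. Adding a change from Week 0 to the listing would write in a derivation that Table 11 does not call for. What remains is a labelling risk for PGI-S and CGI-C that rests on an unstated decoding step. A programmer listing collected responses would ordinarily use the wording held in the eCRF or the device data.

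**Conclusion.** No change to the plan follows. Protocol 9.4.2 contains a one-word clerical slip (PGI-C for CGI-S), Table 3 a wrong cross-reference, and the SAP response lists that do not match the protocol's instruments, in text whose derivations are no longer run. Each can be resolved from the protocol's own schedule and instrument descriptions.

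Size: 0 CGI-S values shown to be lost; 0 estimates, tests or conclusions altered; at most 12 randomized patients in descriptive listings. Wrong PGI-S labels could affect 0 to 3 of the 4 response options, and CGI-C labels up to 6 of 7, but only if the old SAP lists were used for decoding.

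This rests on two assumptions: that sites follow Table 3 and Section 8.1.4 for Part D, and that the Table 11 listings show responses as collected. Neither the eCRF nor the device coding is in the documents, so the second cannot be confirmed; nothing in them points the other way.
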